Recently developed non invasive techniques are more reproducible and reliable for the detection of early dysfunction of small fibers. One of these new techniques involves the measurement of **dermal electrochemical conductance** (**DEC**) or sudomotor dysfunction index and has been evaluated by well-designed studies (Calvet, Dupin, Winiecki, Black, 2013; Casellini 2013; Devigili 2008; Peltier 2009) which support its use as a screening test (20).

Ramachandran *et al* (21) studied the use of DEC to detect diabetes and other disorders of glucose metabolism. In a study on the use of DEC Casellini *et al* (5) applied a PN test which showed a low sensitivity of 78% and a specificity of 92% in diabetic patients without neuropathy compared to other subjects with neuropathy and a control group. In this latter study, correlation with clinical parameters showed adequate reproducibility of the results, particularly in regard to the measurements of the feet (5). Several other studies (22) also obtained significantly lower DEC values on comparing diabetic patients and controls. In a study of patients following a 12-month program of intense physical activity, Raisanen *et al* (23) observed a greater improvement in DEC compared to weight, waist circumference or maximum oxygen volume (VO₂ max).

Therefore, taking into account the large number of methods used and the learning curve required to correctly implement these techniques as well as the absence of consensus as to which method is the most adequate to diagnose DSPN, the aim of this study is to validate the usefulness of DEC measurement in the early diagnosis of DSPN compared with traditional techniques in the Primary Care setting.

HYPOTHESIS AND OBJECTIVES

The hypothesis of our study is that the measurement of DEC is feasible, sensitive and specific and more or equally effective to other techniques commonly used in the initial screening of diabetic neuropathy in Primary Care.

Main objective

To evaluate the feasibility, effectiveness and performance of a new technique which measures DEC (sudomotor reflex) in the screening of diabetic neuropathy in Primary Care.

Specific objectives

1. Determine the performance of DEC (quantitative assessment of sudomotor reflex) as a tool for the screening of diabetic neuropathy in Primary Care compared with the Semmes-Weinstein 5:07 MFT when an EMG is used to confirm the presence of diabetic peripheral neuropathy in patients with prediabetes and type 2 diabetes.

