To estimate the validity and performance of a screening test that showed a sensitivity of 82%, a precision of 9% and a confidence interval of 95% (CI95%), considering a loss percentage of 20%, this study will include a total of 160 participants. The proportion of diabetes / prediabetes / normal glucose tolerance will be 2:1:1. The contribution by centres will be: 66% from the Mutua de Terrassa (106 cases) and 34% from Reus (54 cases).

Variables and dynamic data collection:

After verifying the inclusion criteria and receiving written informed consent to participate, during the **first visit** to the Primary Care centres the medical history of the patient will be obtained and a physical examination will be performed using the MFT and the NDS and UENS questionnaires will be given to screen for PN. The patient will also undergo DEC quantification using the Sudoscan® device.

The following variables were collected:

- Age, sex and country of origin.

- Family history of type1 or type2 DM: (yes / no).

- In diabetic population, length of diabetes evolution (in years) since diagnosis.

- Toxic habits: smoking (active smoker / ex smoker / non-smoker); drinking (teetotal, occasional drinker, habitual drinker).

- Other complications of diabetes and year of diagnosis (retinopathy, ischemic heart disease, peripheral vascular disease, cerebral vascular disease and diabetic nephropathy) will be collected from the patient medical records.

- Diabetes treatment.

- Other pharmacological treatments related to: hypotension, hypolipidemia, arterial thrombosis, among others.

On physical examination the following variables will be collected:

- Anthropometric data: Height (cm), weight (kg) (using validated clinical scale with stadiometer in light clothing), waist circumference (cm) (using a flexible measuring tape), measuring the point between the navel and upper iliac crest.

- Systolic/diastolic blood pressure; presence of pulses in pedia/posterior tibial arteries. Blood pressure (mmHg) measurements will be made three times while seated after 30 minutes of rest using a validated automatic device, with each measure being made at least one minute apart. The data recorded will be the mean of the second and third readings.

Other data to be collected include:

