The Chi-square test will be used to analyse qualitative variables and the Student t-test will be performed for quantitative variables. Logistic regression will be used to identify predictors of diabetic neuropathy. Dependent variables (Response) will include the presence of diabetic neuropathy diagnosed by EMG or the NDS / UENS questionnaires. We will compare the performance of DEC with that of the MFT as screening tests of PN.

To determine the validity and reliability of DEC we will calculate the sensitivity, specificity, the positive and negative predictive values, and the positive and negative likelihood ratios. A ROC curve will be used and the area under the curve will be calculated. A p value <.05 will be considered as statistically significant. The analysis will be performed with the statistical packages STATA/SE 12.0 and R for Windows.

LIMITATIONS OF THE STUDY

The main limitation of the present study is accurate diagnosis of diabetic neuropathy since some studies have shown that some cases of diabetic neuropathy present no alterations in the EMG. Indeed, several considerations should be taken into account. Firstly, the EMG test is more specific, albeit not very sensitive, showing positive results in advanced stages of PN. The fingerboard and the NDS questionnaire are commonly used for the diagnosis of diabetic neuropathy, probably because the NDS is carried out prior to EMG and is actually often used to avoid the need for EMG. Therefore, both the EMG and the NDS score, which mainly assess the dysfunction of myelinated fibers provide a good profile for diagnostic confirmation. On the other hand, both the DEC and the MFT are able to diagnose and stage diabetic neuropathy earlier than the previous two tests by the detection of unmyelinated fiber dysfunction. But, another limitation is that MFT is a good test for prediction of a foot ulcer but is certainly insensitive for the detection of early neuropathy. For this reason, we think about the UENS, because of its sensitivity to early sensory loss and ability to record modest anatomic change in sensory function, considering patients with milder neuropathy. Therefore for purposes of simplification and taking into account the possible limitations, we will compare the effectiveness of the measurement of DEC and the use of MFT as diagnostic tools in Primary Care according to whether the true diagnosis is achieved by a) the EMG or b) the score of the NDS or UENS questionnaires.

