Obviously there are another tests to detect early neuropathy, i.e. the Norfolk QOL-DN scale; but this questionnaire is not practical in the clinical scenario. Certainly, this test is a good tool to detect unaware neuropathy in patients with diabetes (24). This study used the Norfolk QOL-DN scale on 25000 patients with diabetes and found 6600 patients who were not aware of their neuropathy nor did their physicians know.

17

Another limitation of this study is the possibility of introducing a selection bias, and thus, we will consecutively include patients with type 2 DM, excluding patients with type 1 DM. We will also include a group of patients without DM or other glucose homeostasis disorders matched by age and gender to a 2:1:1 ratio (80 with DM, 40 with prediabetes and 40 with normal glucose tolerance).

QUALITY ASPECTS

This project will promote a strategy to determine whether the implementation of a new technique simplifies the detection of a major complication of diabetes, such as neuropathy.

Primary Care is clearly the most appropriate setting for the screening of this complication. Indeed, the earlier the diagnosis the better the prognosis. This strategic action on health is directly linked to:

(A) New medical technologies to promote personalized medicine based on the profiles of the individuals and not the disease.

(B) Translational and clinical research, evidence-based scientific and technological knowledge.

(C) Validation of a promising new technology for early detection of diabetic neuropathy in Primary Care.

(D) Application of evidence in clinical practice. This is a validation study of diagnostic technology implemented in real life conditions which would provide additional knowledge for everyday clinical practice.

It is of note that this study will also determine the cost-effectiveness of this new tool which is essential for the validation of new technologies aimed at different healthcare areas such as Primary Care.

Additionally, this project will establish synergies at different levels such as Primary

Care and Neurology, and the results can be shared with a number of centers, primary care areas and different scientific societies involved in the comprehensive care of patients with diabetes.

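### The accuracy analysis of DEC ignores glycaemic group, so figures pooled over the 2:1:1 mix may partly reflect differences between groups

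*Combined protocol and SAP*

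**What the plan says.** The Statistical analysis section lists the usual accuracy measures for DEC, states that "A ROC curve will be used and the area under the curve will be calculated", and announces a comparison of DEC with MFT. It does not say which participants enter these analyses. It mentions no stratification or adjustment by glycaemic status. The logistic regression in the same section looks for predictors of neuropathy and is not tied to the ROC curve.

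The mix is set by design. Under Sample size, "The proportion of diabetes / prediabetes / normal glucose tolerance will be 2:1:1"; Limitations gives the counts as "80 with DM, 40 with prediabetes and 40 with normal glucose tolerance". The groups are matched on age and gender only.

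The Introduction cites a study that "studied the use of DEC to detect diabetes and other disorders of glucose metabolism" and others that "also obtained significantly lower DEC values on comparing diabetic patients and controls". It also says that the prevalence of neuropathy increases with diabetes.

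Specific objective 1 is narrower than the recruited sample. It compares DEC with MFT "when an EMG is used to confirm the presence of diabetic peripheral neuropathy in patients with prediabetes and type 2 diabetes". Objective 2 names the same two groups, with UENS as the reference. Neither mentions the normal-glucose controls. The main objective has no glycaemic restriction, and the sample-size paragraph applies to all 160 participants.

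**The concern.** A pooled ROC curve compares every reference-positive patient with every reference-negative patient, including pairs from different glycaemic groups. Suppose neuropathy is commoner in diabetes and DEC is lower in diabetic patients even when the reference test is negative. Many of the cross-group pairs are then ordered correctly because of group membership, not because DEC separates neuropathy from no neuropathy among similar patients. The AUC rises for that reason, and a cut-off chosen on the mix has lower specificity in the diabetic patients than the pooled figure suggests.

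This differs from the dependence of predictive values on prevalence: re-weighting the predictive values would not remove it. At stake are the AUC and specificity quoted for DEC, the false-positive rate among diabetic patients who are screened, and the fairness of the DEC-versus-MFT comparison if the two tests vary with glycaemic group to different degrees.

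**Working it through.** The plan gives no AUC and no DEC distribution by group, so there is no figure of its own to reproduce. The check shows how large the effect could be.

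**Inputs from the documents.** Group sizes 80/40/40. Neuropathy prevalence in diabetes 24.1% (the Spanish study) to 59% (type 2 diabetes, the Rochester study), both in the Introduction. Losses of 20%, which leave 160 × 0.8 = 128 evaluable (64/32/32).

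**Assumptions.** The score is DEC with its sign reversed, normal with unit SD. Among reference-negative patients its mean is d in diabetes, d/2 in prediabetes and 0 in controls, with d = 0.5 to 1.0. Prevalence is 12-25% in prediabetes and 5-10% in controls. Cases are shifted by δ in every group, with δ = √2·Φ⁻¹(0.70) = 0.742, so the within-group AUC is 0.70.

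**Formula.** With c_i the share of cases in group i and k_j the share of non-cases in group j, pooled AUC = Σ_i Σ_j c_i k_j Φ((μ_i + δ − μ_j)/√2).

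**One case in full: prevalence 40/20/5%, d = 1.**
- Cases 32, 8, 2 (shares 0.762, 0.190, 0.048). Non-cases 48, 32, 38 (shares 0.407, 0.271, 0.322).
- Diabetes cases against non-cases with diabetes, prediabetes and normal glucose: 0.700, 0.810, 0.891; weighted 0.791.
- Prediabetes cases: 0.568, 0.700, 0.810; weighted 0.682.
- Control cases: 0.428, 0.568, 0.700; weighted 0.55.
- Pooled AUC = 0.762 × 0.791 + 0.190 × 0.682 + 0.048 × 0.55 = 0.76, against 0.70 within every group.
- Diabetes plus prediabetes only: case shares 0.8 and 0.2, non-case shares 0.6 and 0.4. AUC = 0.8 × (0.6 × 0.700 + 0.4 × 0.810) + 0.2 × (0.6 × 0.568 + 0.4 × 0.700) = 0.72.
- Specificity: the cut-off t solves Σ k_j Φ(t − μ_j) = 0.85, so t = 1.672. Specificity in diabetes is Φ(0.672) = 75%, against Φ(1.672) = 95% in controls. With controls left out it is 81% in diabetes.

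**Range**, with the low diabetes prevalence paired with the low prediabetes prevalence and high with high:

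| | All three groups | Prediabetes + type 2 diabetes |
|---|---|---|
| Within-group AUC 0.70 shows as | 0.72-0.78 | 0.71-0.73 |
| Specificity in diabetes when pooled specificity is 85% | 73-80% | 80-83% |

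Pairing 59% in diabetes with only 12% in prediabetes stretches the AUC maxima to 0.79 and 0.75.

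**Equal prevalence.** With 24.1% in every group, 0.70 pools to 0.69-0.70, so the AUC is not inflated. The specificity gap does not need unequal prevalence, because it is computed from reference-negative patients alone.

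**MFT.** If its sensitivity and false-positive rate are the same in every group, pooling changes neither. If instead sensitivity is 0.75/0.65/0.55 and the false-positive rate 0.25/0.15/0.05 (assumed), the mean of sensitivity and specificity is 0.75 within each group but 0.78 pooled.

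**Precision.** Simulated samples of 128 at 40/20/5% and d = 1 give an AUC SD of about 0.047-0.049 pooled, 0.057-0.059 group-adjusted and 0.067 in diabetes alone. Prediabetes alone would hold 32 × 0.12 ≈ 4 to 32 × 0.25 = 8 cases.

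**The case against.** The strongest reply is that the plan never says it will pool all 160 participants. A reader might infer that from the single ROC sentence and the sample-size paragraph, but the section is silent, and objectives 1 and 2 point to prediabetes plus type 2 diabetes. There the inflation is about 0.01-0.03, smaller than the sampling SD. This stands as to size. It does not remove the point: the population is left open, and sampling error does not cancel a bias of this kind.

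A reader might also infer that DEC is shown to fall with diabetes itself. The documents do not show this. The cited contrasts compare diabetic patients with controls and are not restricted to people free of neuropathy, so a pure neuropathy test could give the same result. What makes a shift among reference-negative patients plausible is the protocol's own account of EMG as insensitive to early disease and of DEC as detecting it earlier. EMG-negative diabetic patients may then have low DEC because of early neuropathy that EMG misses. The shift would be real, but its cause and size are unknown.

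Nor do the documents support saying that MFT gets no such benefit, since nothing describes MFT by glycaemic status. The claim that DEC would be detecting diabetes rather than neuropathy is also too strong, because under these assumptions the effect is a partial inflation.

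Equal prevalence would remove the AUC inflation. The Introduction's statement that neuropathy rises with diabetes, and the exclusion of neuropathy not related to diabetes, make equality across all three groups unlikely. Finally, a pooled AUC is a legitimate description of a mixed population. But this mix is fixed at 2:1:1 by design, and the plan does not present it as the target population.

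**Conclusion.** The point holds in a limited form. The plan leaves the ROC population open and does not condition on glycaemic group, although its own background links that group to both the test and the target condition. Accuracy pooled over the mix may therefore be partly between-group separation. Under the stated assumptions the AUC is overstated by about 0.02-0.08 over all three groups and 0.01-0.03 in the objectives' population, starting from 0.70. Specificity in diabetes would be 5-12 points below a pooled 85% with controls included, or 2-5 points without them. The shift and the prevalences outside diabetes are assumed, not documented. Direction and size depend on them, and the effect on the DEC-versus-MFT comparison could go either way. This should be changed, because the plan can condition on group using data it already collects.

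**What to change.** In the Statistical analysis section:

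- State that the accuracy analysis of DEC and MFT uses the population of objectives 1 and 2, prediabetes plus type 2 diabetes, and that normal-glucose controls are used descriptively.
- Report sensitivity, specificity and AUC of both tests within type 2 diabetes.
- For any combined figure, and for the DEC-minus-MFT difference, use a group-adjusted AUC: compare each case only with reference-negative patients of the same glycaemic group and average over cases.
- Report prediabetes alone only descriptively, since it may hold about 4-8 cases.

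Glycaemic status is already recorded, so the change takes a few lines of text and code. The price is precision. With 128 evaluable patients the AUC SD rises from about 0.047-0.049 pooled to 0.057-0.059 adjusted, roughly 45% more variance ((0.059/0.049)² = 1.45), and to about 0.067 in diabetes alone. The AUC reported for DEC will probably be less favourable.
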